#### 17. Efficacy Evaluations

#### 17.1. Data Sets Analysed

The principle of intention-to-treat, as far as practically possible, will be the main strategy of the analysis adopted for the primary outcome and all secondary outcomes. These analyses will be conducted on all randomised participants, in the group to which they were randomised, and for whom the outcome(s) of interest have been observed/measured. No imputations will be made.

#### 17.2. Demographic and Other Baseline Characteristics

Descriptive statistics will be presented split by treatment group and overall. Categorical data will be summarised by frequencies and percentages to one decimal place. Continuous data will be summarised to one decimal place by mean (standard deviation), median (interquartile range) and

#### Form prepared: 16/04/2024 v2.0 for BESS Page 14 of 30

range, irrespective of distribution. No formal statistical testing will be undertaken, but the clinical significance of any imbalance will be noted.

Baseline variables to be included:

- Whether infant premature or term-born
- Age/corrected age at randomisation
- Sex
- Weight
- Whether infant intubated upon arrival at PICU
- Whether infant on oxygen supplementation upon arrival at PICU
- Time on MV prior to randomisation
- Underlying viral/bacterial infection

# 17.3. Compliance with treatment

Accountability logs and treatment CRFs will be assessed to determine treatment compliance. For each dose, the number of participants expected to receive the dose and the number and percentage actually receiving the full dose will be summarised by allocated treatment group and overall. Reasons for participants not receiving doses will be presented.

# 17.4. Analysis of efficacy outcomes

# 17.4.1. Primary Outcome: Total duration of mechanical ventilation

The primary outcome will be estimated by calculating the time from randomisation to final extubation (including any time off MV due to failed extubation) to assess if there is any evidence of a difference in the time between arms.

An attempt to extubate is deemed to have failed if the participant is re-intubated within 48 hours of the most recent extubation. If a participant is re-intubated within 48 hours of the most recent extubation their follow-up should continue until a successful intubation.

# 17.4.1.1. Derivation

The duration of mechanical extubation will be calculated by identifying the date and time (OAODATXD) associated with final extubation as indicated by OAOOUTCC = "Successful" on the Observations and Outcomes CRF. The difference between the date/time of randomisation taken from the Almac randomisation log and the date/time of successful extubation will be calculated in hours and transformed using natural logarithms.

# 17.4.1.2. Analysis

Descriptive statistics will be presented split by treatment and overall for the time from randomisation to final successful extubation (before the data is transformed) and time off MV due to failed extubation. The summaries will be presented as median and interquartile range as the data is likely to be skewed.

A comparison of group means will be conducted using a two-sample t-test on the log transformed data (the log transformation will be done using natural logarithms). The between group difference of the log transformed data will then be back transformed by taking the exponent to give the geometric mean difference and the corresponding 95% confidence interval.

A linear mixed effects model will also be fitted on the log transformed data, using ANCOVA to test for a difference between groups with adjustment for the stratification factor of time on ventilation prior to randomisation (<24h and  $\geq$ 24h), sex and adjusted age at enrolment as a fixed effects and site as a random effect (random intercept only). The exponentiated between-group difference and corresponding 95% confidence interval will be reported.

The approach to the primary outcome analysis will be a compete case analysis and will only include those participants for which the primary endpoint has been observed. If there are any participants who have not recorded a successful extubation at the point at which they were last followed up (e.g. consent for follow up has been withdrawn) then sensitivity analysis will be conducted including these participants to assess the robustness of the primary outcome analysis.

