11.5 Analysis Plan

A full SAP will be written prior to the conduct of any comparative analysis of the treatment arms. The main features of the SAP are included here.

The primary analysis will be a test of the difference in geometric mean durations of MV between groups (placebo vs. poractant alfa), reported with the corresponding 95% confidence interval. The analysis will be conducted according to the intent-to-treat principle, and will incorporate the stratification factors of duration of ventilation (<24hrs and >=24hrs) prior to randomisation and site.

For the secondary outcomes, longitudinal data for VI, OI, OSI and SF will be analysed with joint modelling. LRSQ data will be modelled longitudinally and comparisons made between groups. Binary data will be reported in terms of relative risk with 95% confidence intervals.

Within BESS, data will be collected as to ascertain readiness for spontaneous breathing test and time of extubation.

As much information as possible will be collected about the reasons for missing outcome data; this will be used to inform any imputation approaches employed in the analysis. Such methods will be fully described in the SAP.

IRAS 220853 Page **63** of **87**

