# 5. Statement of Compliance

This Statistical Analysis Plan (SAP) provides a detailed and comprehensive description of the preplanned final analyses for the study "BESS". The planned statistical analyses described within this document are compliant with those specified in brief within the BESS protocol v3.0 (31/07/2019). These analyses will be performed by the trial statistician.

This study is carried out in accordance with the World Medical Association Declaration of Helsinki (1964) and the Tokyo (1975), Venice (1983), Hong Kong (1989) and South Africa (1996) amendments and will be conducted in compliance with the protocol, Liverpool Clinical Trials Centre (LCTC) Clinical Trials Unit (CTU) Standard Operating Procedures (SOPs) and EU Directive 2001/20/EC, transposed into UK law as the UK Statutory Instrument 2004 No 1031: Medicines for Human Use (Clinical Trials) Regulations 2004.

This study is a clinical trial of a medicinal product and is registered on the EudraCT database. This SAP has been developed to support the posting of results on the EudraCT system. This is a regulatory requirement which should be fulfilled within 6 months after the end of the study as defined within the clinical trial protocol. The results of the final analysis described within this SAP will be contained within a statistical analysis report. This report will be used as the basis of the primary research publications according to the study publication plan.

All analyses are performed with standard statistical software (SAS v9.4 or later) with the exception of the joint modelling analysis which will be performed using the JoineR package [5] package in R. The finalised analysis datasets, programs and outputs will be archived following Good Clinical Practice (GCP) guidelines and SOP GE012 Archiving procedures. The testing and validation of the statistical analysis programs will be performed following SOP ST001.

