#### 8.7. Method of assignment to treatment

Participants will be randomised to receive either poractant alfa or air placebo in a 1:1 ratio. The randomisation list will be generated by an independent statistician at the LCTC who is not otherwise involved in the BESS trial. Randomisation lists will be computer-generated using block randomisation, stratified by site and duration of ventilation (<24hrs and >=24hrs) prior to randomisation.

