# 17.4.2.2. Analysis

Descriptive statistics will be presented split by treatment and overall for the time from randomisation to readiness for SBT (before being transformed). The summaries will be presented as median and interquartile range as the data is likely to be skewed.

The frequency and percentage of the number of times each participant is recorded as meeting the criteria for readiness for SBT will presented split by treatment and overall.

The comparative analysis will be as described in 17.4.1.2 but will just involve the two-sample t-test, a linear mixed effects model will not be used for this outcome.

A sensitivity analysis will be conducted using the first time a patient meets the numerical criteria for SBT. The sensitivity analysis will be as described in 17.4.1.2 but will just involve the two-sample t-test, a linear mixed effects model will not be used for this outcome.

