## 18. Missing data and withdrawals

Missing data will be quantified for all outcomes presented in the final analysis report. Where known, reasons for missingness will be given.

Withdrawals from trial will be summarised and presented as line listings detailing:

- 1. Site
- 2. Time from randomisation to withdrawal
- 3. Decision to withdraw participant made by:
  - a. Clinician
  - b. Parent/person with parental responsibility
  - c. Both clinician and parent/person with parental responsibility
- 4. Reason for withdrawal:
  - a. Death
  - b. Lost to follow-up
  - c. Transfer to non-participating site
  - d. Withdrawal of consent for follow-up
  - e. Other (specify)

Every effort will be made to collect follow-up data even in the event of participants discontinuing the trial intervention. In the case of withdrawals from study, available data will still be included using an intent-to-treat approach.

#### 19. Additional analyses Additional analysis 1

A sensitivity analysis of the primary analysis will be done to assess the robustness of the primary analysis. This will be done using a Cox proportional hazards model and will allow the censoring of patients who do not observe the primary endpoint of successful extubation. The start-point and end point for patients having the event of successful extubation will be the same as those defined in section 17.4.1.1. For patients who do not have a successful extubation recorded these will be censored at the last date and time (OAODATXD) an observation is recorded on the Observations and Outcomes CRF. The cox proportional hazards model will include the allocated treatment and time on ventilation prior to randomisation as covariates.

#### Additional analysis 2

A subgroup analysis of the primary outcome will be undertaken, This was based on a recommendation from the Trial Steering Committee who met on the 20th February 2024.

The subgroup analysis will examine the primary outcome stratified by whether the baby was born prematurely or not and will include an interaction term between treatment and prematurity in the linear mixed effect model described in 18.4.1.2.

Results will be presented from the model with the interaction result alongside.

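### SAP 17.4.1.2 sets out an unadjusted t-test and a stratification-adjusted mixed model for the primary outcome and does not say which one decides the trial

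*SAP*

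**What the plan says.** **Protocol 11.5.** "The primary analysis will be a test of the difference in geometric mean durations of MV between groups", by intention to treat, and this analysis "will incorporate the stratification factors of duration of ventilation (<24hrs and >=24hrs) prior to randomisation and site". These are the two factors used in the randomisation (protocol 7.3 and 11.2). SAP 8.7 confirms that the lists are "stratified by site and duration of ventilation (<24hrs and >=24hrs) prior to randomisation".

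**SAP 17.4.1.2.** Two comparisons are listed in turn. The first: "A comparison of group means will be conducted using a two-sample t-test on the log transformed data". It contains no stratification factor, and its back-transformed result is the one described as the geometric mean difference, with a 95% confidence interval. The second: "A linear mixed effects model will also be fitted on the log transformed data". It has prior-ventilation stratum, sex and adjusted age as fixed effects and a random intercept for site, again with an exponentiated difference and a 95% confidence interval. Neither is labelled primary, supportive or sensitivity.

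**Elsewhere in the SAP.** Section 19 (Additional analysis 1) introduces the Cox model with "A sensitivity analysis of the primary analysis will be done to assess the robustness of the primary analysis" and does not identify which analysis is meant. Additional analysis 2 builds the prematurity interaction on the mixed model. Section 21 has an independent statistician program the primary analysis. Section 12 plans no multiplicity adjustment. Section 5 describes the planned analyses as "compliant with those specified in brief within the BESS protocol v3.0 (31/07/2019").

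**The concern.** A confirmatory SAP should settle, before allocation is known, which single result answers the primary question. This one yields two estimates and two intervals for that question, with no rule for the case where they fall on opposite sides of 5%. A p-value of 0.06 from one and 0.04 from the other would leave the conclusion contestable. The Cox sensitivity analysis and the independent programming check also refer to a primary analysis that the reader cannot identify.

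The order adds to the difficulty. The t-test comes first and carries the geometric-mean wording used in the protocol, while the model follows with the word *also*, so the unadjusted test looks like the lead. It leaves out both factors that protocol 11.5 attaches to the primary analysis. Under stratified allocation, omitting prognostic strata gives a standard error that is too large.

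**Working it through.** **1. What each text supplies**

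| | Protocol 11.5 | SAP t-test | SAP mixed model |
|---|---|---|---|
| Compares geometric means | yes | yes | yes |
| Prior-ventilation stratum | yes | no | yes |
| Site | yes | no | yes (random) |
| Sex, adjusted age | not named | no | yes |
| Called primary | yes | no | no |

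An analysis containing both stratification factors is therefore planned. What is missing is its designation.

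**2. Reproducing the sample size.** Inputs from protocol 11.3: means 4.83 and 4.08 days, SD 2.5 in each group, two-sided alpha 0.05, equal allocation, 5% dropout.

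- Log-scale variances, ln(1 + CV²): ln(1 + 0.5176²) = 0.2374 and ln(1 + 0.6127²) = 0.3188.
- Difference in log means: ln(4.08/4.83) − ½(0.3188 − 0.2374) = −0.1687 − 0.0407 = −0.2095 (to rounding), a geometric mean ratio of 0.811.
- Average log SD: √[(0.2374 + 0.3188)/2] = 0.5273.
- n per group = 2 × 0.5273² × (1.960 + z)² / 0.2095². This gives 133.2, so 134, for 90% power (z = 1.2816), and 99.5, so 100, for 80%.
- 134/0.95 = 141.05, so 142 per group and 284 in total.

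All the stated figures reproduce. The calculation has no covariate term, so it corresponds to an unadjusted comparison of log means.

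**3. What ignoring the strata costs.** Let R² be the share of log-duration variance explained by the stratification factors alone. The documents give no value, so 5%, 10% and 20% are assumptions. With allocation balanced within strata, the treatment difference has true variance proportional to 1 − R², but the t-test estimates it as if R² were 0. Writing s = √(1 − R²), and using 1.960 + 1.2816 = 3.2415 (to rounding) as the standardised effect at 90% power:

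- t-test true alpha = 2[1 − Φ(1.960/s)]
- t-test power = Φ(1.2816/s)
- adjusted power = Φ(3.2415/s − 1.960)
- extra infants the t-test would need to match = [1 + 1.960(1 − s)/3.2415]² − 1

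| R² (assumed) | s | t-test alpha | t-test power | Adjusted power | Equivalent gain in n |
|---|---|---|---|---|---|
| 5% | 0.975 | 4.4% | 90.6% | 91.4% | 3% |
| 10% | 0.949 | 3.9% | 91.2% | 92.7% | 6% |
| 20% | 0.894 | 2.8% | 92.4% | 95.2% | 13% |

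Starting from the 90.2% power that 134 per group actually gives moves the powers by at most 0.2 percentage points.

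**4. Rough check by simulation.** The set-up was 268 infants, 14 sites by 2 strata, permuted blocks, with site and stratum fitted as fixed effects. At R² = 20% the t-test had alpha 3.0% and power 91.8%; the adjusted analysis had 4.9% and 94.7%. With 4,000 null trials the Monte Carlo standard error is about 0.3 points. At R² = 0, where both tests should give 5%, the run returned 5.8% and 6.0%, so it supports the pattern rather than the decimals.

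**5. Choosing the more favourable result.** If the adjusted analysis contains only the stratified factors, declaring success when either test is significant gave simulated alpha of 4.7% to 5.2% for R² of 10% to 30%. If the covariates are not balanced by design, the corresponding calculation gives 6.5% to 7.6%.

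**The case against.** The strongest reply is that nothing is missing. The mixed model contains both stratification factors, is reported with its interval, and already underlies the prematurity subgroup analysis. Order is not designation, so placing the t-test first does not make it primary. Both analyses are prespecified, the t-test errs on the safe side, and 284 infants suffice under either. All of this stands, and it confines the point to designation.

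Four stronger readings are tempting, and the documents do not support them.

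- *That the SAP breaches the protocol.* The chronology in the supplied protocol ends at version 2.0. The SAP declares compliance with version 3.0, and its change-control table lists protocol 6.0. Section 11.5 of those versions is not available here. Even against the supplied text, there is a departure only if the t-test is intended as primary.
- *That the t-test loses alpha down to 2.8% and the model is also worth up to 25% more infants.* These need different assumptions. The alpha loss comes only from variance explained by the stratified factors, and then the gain is 3% to 13%. A gain of 1/(1 − R²) − 1, that is 5%, 11% or 25%, requires covariates that are not stratified, such as age and sex. Omitting those leaves the t-test at its nominal alpha.
- *That choosing between the two results seriously inflates the type I error.* The inflation is negligible for stratified covariates and modest otherwise.
- *That the secondary outcomes share the fault.* For readiness for a breathing test, for example, the comparison "will just involve the two-sample t-test, a linear mixed effects model will not be used for this outcome". Protocol 11.5 attaches the stratification factors to the primary analysis only. SAP 17.4.5.1 and 17.4.7.1 also allow durations of zero, which have no logarithm, so the same log-scale model could not simply be carried over.

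**Conclusion.** The point holds as a gap in designation. SAP 17.4.1.2 offers two analyses of the primary outcome and does not say which one governs, while sections 19 and 21 rely on that being known. Whether there is also a departure from the protocol depends on which analysis is intended and on the later protocol text.

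The statistical cost of leading with the t-test is real but limited: a conservative test, an interval that is too wide, and roughly 1 to 3 percentage points of power for R² between 5% and 20% (91.4 − 90.6 = 0.8; 95.2 − 92.4 = 2.8). These sizes rest on assumed R² values, close balance within strata and a normal approximation. Any variance explained by age and sex would add power to the model without lowering the t-test's alpha. The reason to act is less the power than the need for one decisive result fixed in advance.

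**What to change.** Before allocation is released to the statistical team, amend SAP 17.4.1.2 to state that:

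- the mixed model already specified there (treatment, prior-ventilation stratum, sex and adjusted age as fixed effects; site as a random intercept) is the single primary analysis;
- its 95% confidence interval and p-value decide the trial;
- the unadjusted t-test is supportive;
- sex and adjusted age are prespecified covariates in addition to those named in protocol 11.5.

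Check the wording against section 11.5 of the current protocol version, and have SAP sections 19 and 21 refer to the analysis so named.

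The cost is a few sentences. No new model or data item is needed, and the sample size does not change. Adjusting the secondary duration outcomes and adding site to the Cox model are optional and not part of this point.

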3.6.2 Secondary Outcomes/Endpoints

The secondary outcome measures for the trial (WP-A) are:

For efficacy:

- 1. duration of post-extubation non-invasive respiratory support (all forms of non-invasive ventilation: e.g. nasal CPAP and nasal high low oxygen)
- 2. duration of oxygen supplementation
- 3. number of trial interventions given (both poractant and placebo)
- 4. use of steroids to assist extubation
- 5. duration of stay on PICU and in hospital;
- 6. change over time from baseline of Ventilation Index (VI), Oxygenation Index (OI) and Oxygenation Saturation Index (OSI) while mechanically ventilated, & SpO₂/FiO₂ (SF) ratio.¹
- the score (value) of parent reported outcome measure of respiratory symptoms the "Liverpool Respiratory Symptom Questionnaire" (LRSQ) at 6m (+/-1m) and 12m (+/-1m) (20);

IRAS 220853 Page **20** of **87**

¹ VI and OI are validated physiological measurements reflecting respiratory function (gas exchange) normalised for level of respiratory support provided by MV, but require blood sampling(21). OSI is a validated physiological measurement reflecting respiratory function (gas exchange) normalised for level of respiratory support provided by MV that does not require blood sampling (41). The SF ratio is a non-invasive measure of respiratory function and can be calculated in situations where invasive blood gas monitoring and MV has ceased (22).

8. time from randomisation to meeting study criteria for readiness for Spontaneous Breathing Test

For safety:

- 1. failure to administer the intervention due to any adverse event during preparatory processes (tracheal toilet or BAL)
- 2. failure to complete administration of the intervention due to any adverse event during administration of the intervention (regardless of which arm of allocation)
- 3. incidents of 'air leak' (pneumothorax and pneumomediastinum) occurring before discharge from PICU
- 4. other adverse events and serious adverse events associated with the intervention
- 5. any need to replace the endotracheal tube
- 6. parent reported readmission to hospital (all causes) up to 90 days post randomisation
- 7. death during PICU admission
- 8. all-cause mortality at 90 days post randomisation

IRAS 220853 Page **21** of **87**

Table 1: Objectives and Outcome Measures

Objectives	Outcome Measures	Timepoint(s) of evaluation of this outcome measure (if applicable)

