8.4 Procedures for assessing Efficacy

8.4.1 Efficacy Assessment 1

Efficacy will be assessed by group-wise comparison of the primary outcome measure group "Duration of MV after randomisation" by intention to treat. This is defined as time from randomisation to final extubation in hours, including any time off MV where the infant requires reintubation for a further period of MV. Time of randomisation and intervention will be recorded in the patients' notes and CRFs. MV ceases at extubation, an event when the endotracheal tube (breathing tube) is removed and the infant is allowed to breathe without invasive mechanical support. Extubation is an important discrete event in a patient's care pathway, is routinely recorded in the notes and PICANet audit.

8.4.2 Efficacy Assessment 2

The Ventilation Index (VI), Oxygenation Index (OI), Oxygenation Saturation Index (OSI) and SF ratio are secondary outcomes of efficacy derived from blood gas results (capillary blood gas sampling times as per Table 2 Schedule for intervention and follow-up), ventilator settings, and non-invasive monitoring. These data are captured through existing intensive care automated monitoring process or regular manual entry on large format (broad-sheet) bed-charts. This data will be transcribed by the research nurse to the CRF.

Mechanical Ventilation parameters to allow calculation of VI, OI, OSI and SF ratio must be recorded at the corresponding time when Blood Gas samples are scheduled to be taken for research or taken for routine purposes.

Mechanical Ventilation parameters are recorded regularly for ventilated patients as part of standard care. BESS does not require site teams to take any additional readings of these parameters for study purposes, but **all blood gas and ventilator readings** taken as part of standard care must be transcribed into the CRF to allow for calculation of these ratios over time.

After extubation, all inhaled Oxygen and peripheral oxygen saturation parameters recorded as part of standard care must be transcribed into the CRF to allow for calculation of this ratio over time. Blood gas indices and ratio definitions are as follows:

- VI = (PaCO₂ × (PIP-PEEP) × respiratory rate)/1,000
- OI = $(MAP \times FiO_2 \times 100)/PaO_2$
- OSI = $(MAP \times FiO_2 \times 100)/SpO_2$
- SF = SpO₂/FiO₂

MAP = mean airway pressure

PaCO₂ = partial pressure of arterial carbon dioxide

 FiO_2 = Fraction of air inspired that is oxygen

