11.3 Sample Size calculation

The study will be powered to detect a minimally clinically important difference of 18 hours (0.75 days) in the primary outcome variable of time of mechanical ventilation. Data are expected to be positively skewed, and will therefore be log-transformed, and resulting data back-transformed. The null hypothesis is that of no difference in time of MV between the two groups.

Data from Alder Hey Children's Hospital from an audit of 60 eligible infants admitted to PICU in the seasons 2012/3 and 2013/4 showed a mean (SD) duration of ventilation of 4.83 (2.5) days (PICANet data, 2011-14). Parameters for sample size estimation are therefore as follows:

```
E(Y_1) = 4.83 \text{ and } SD(Y_1) = 2.5 E(Y_2) = 4.08 \text{ and } SD(Y_2) = 2.5 \delta = E(Y_2)/E(Y_1) = 0.845 giving coefficients of variation: \kappa_1 = SD(Y_1)/E(Y_1) = 2.5/4.83 = 0.518 \kappa_2 = SD(Y_2)/E(Y_2) = 2.5/4.08 = 0.613
```

Using the formula of Wolfe and Carlin (1999) with r = 1 for equal allocation and a two-sided alphalevel of 0.05, sample size estimations are 100 per group for 80% power and 134 per group for 90% power.

Taking the sample size of 134 and allowing for 5% dropout requires 142 patients will be recruited to each group, giving a total of 284 participants overall.

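### The adjusted model for the primary outcome leaves out baseline respiratory severity, although it is scheduled for every infant before the first dose; adding it could improve precision at almost no cost

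*SAP*

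**What the plan says.** SAP 17.4.1.2 gives two comparisons for the primary outcome. The first is an unadjusted two-sample t-test on log hours of MV. A linear mixed model is then also fitted, with the prior-ventilation stratum (below 24 h, or 24 h and over), "sex and adjusted age at enrolment as a fixed effects and site as a random effect (random intercept only"). The SAP does not say which of the two is primary. Protocol 11.5 requires the primary analysis to incorporate both stratification factors, and only the mixed model does so.

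No respiratory index is a covariate in that model, in the Cox model or in the prematurity subgroup model (both SAP section 19). None is in the baseline list of SAP 17.2 either. That list does include "Time on MV prior to randomisation", which the model uses only as two categories.

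The severity data are planned. Protocol Table 2 schedules a blood gas and CRF completion before the first intervention. Protocol 8.4.2 says "Mechanical Ventilation parameters to allow calculation of VI, OI, OSI and SF ratio must be recorded" at the scheduled gas times. SAP 17.4.4.1 derives VI, OI, OSI and SF. Protocol 3.6.2 states that "OSI is a validated physiological measurement reflecting respiratory function (gas exchange) normalised for level of respiratory support provided by MV" and that it needs no blood sample.

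**The concern.** By adding sex and age, the SAP already adjusts beyond the stratification factors. It leaves out a pre-dose measure that plausibly bears more directly on time to extubation. Two places in the documents make that link credible. Protocol 8.1.4 identifies readiness for a spontaneous breathing test partly by gas-exchange targets at a given level of ventilation. SAP 17.4.4.2 plans joint models because extubation may be informative drop-out for VI, OI and OSI.

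Two things are at stake. One is the width of the confidence interval for the treatment ratio. The other is protection against chance imbalance in severity, which stratifying by site and prior hours controls only indirectly, if at all. SAP 17.2 promises to note clinically important baseline imbalance, but without a severity index in the table this cannot be done for severity.

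**Working it through.** **Inputs (Protocol 11.3).** Control arm: "mean (SD) duration of ventilation of 4.83 (2.5) days". Treated arm: mean 4.08, SD 2.5 days. Design: "with r = 1 for equal allocation and a two-sided alphalevel of 0.05". Result: "sample size estimations are 100 per group for 80% power and 134 per group for 90% power". Dropout 5%.

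**Step 1: reproduce the plan's figures** with the log-normal formula.
- Log-scale variances, ln(1 + CV²): ln(1 + 0.518²) = 0.2374 for control; ln(1 + 0.613²) = 0.3188 for treated.
- Log-mean difference: ln(4.08/4.83) − (0.3188 − 0.2374)/2 = −0.1688 − 0.0407 = −0.2095, a geometric mean ratio of 0.811.
- n per group = (z₁₋α/₂ + z₁₋β)² × (0.2374 + 0.3188)/0.2095² = 99.5 at 80% power and 133.2 at 90%, rounded up to 100 and 134.
- 134/0.95 = 141.05, so 142 per group and 284 in total.

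All the stated figures match, with no gain from covariates assumed.

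**Step 2: effect of adding a severity covariate.** Let r be its partial correlation with log MV hours, given the covariates already in the model. The residual variance is multiplied by (1 − r²) and the confidence interval width on the log scale by √(1 − r²). At 134 per group:

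Power = Φ(0.2095 / √[(0.2374 + 0.3188)(1 − r²)/134] − 1.96)

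At r = 0 the standard error is √(0.5562/134) = 0.0644, and power is Φ(3.25 − 1.96) = 90.2%. The documents do not give r, so a range is assumed:

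| r (assumed) | Power at 134 per group | CI narrower by | n per group for 90% |
|---|---|---|---|
| 0 | 90.2% | 0% | 134 |
| 0.2 | 91.3% | 2.0% | 128 |
| 0.3 | 92.6% | 4.6% | 122 |
| 0.4 | 94.4% | 8.3% | 112 |
| 0.5 | 96.4% | 13.4% | 100 |

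At the design effect, the 95% CI for the ratio would be 0.715 to 0.920 at r = 0, 0.719 to 0.915 at r = 0.3, and 0.727 to 0.905 at r = 0.5.

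**Step 3: simulation check** (8,000 runs, t-test against ANCOVA). r = 0: 90.0% against 89.8%. r = 0.3: 89.9% against 92.6%. r = 0.5: 89.9% against 96.3%. A useless covariate costs about 0.2 points.

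**Step 4: missing baselines.** If infants without a value were dropped, the effective sample size would be n(1 − m)/(1 − r²), where m is the missing share. The gain is gone once m = r²: 4% at r = 0.2, 9% at r = 0.3, 16% at r = 0.4. For example, r = 0.3 with 10% missing gives 89.9%, below the unadjusted 90.2%. The rule for missing values therefore decides whether the change helps.

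**The case against.** The case for leaving the SAP alone is substantial, and most of its parts stand.

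- **Nothing is broken.** Protocol 11.5 asks only for the stratification factors, and the mixed model has both. A SAP need not justify each covariate it leaves out. This stands, and it makes the point one of efficiency.
- **The benefit rests on an unknown.** A reader might infer that the plan certainly throws away precision, or that about 5 points of power are there for the taking. The documents do not support that: 5 points needs r of about 0.45, and no correlation is given. The exclusions in Protocol 6.2 may also narrow the severity range and so weaken r.
- **The starting point is the unadjusted design.** The 90.2% gives no credit to stratum, sex, age and site. If they already explain some variance, the planned model starts higher and the gain in percentage points shrinks. The proportional narrowing of the interval still follows from the partial correlation.
- **A schedule is not a record.** It is tempting to say that every infant has a pre-dose value. Protocol 8.4.2 requires no ventilator readings beyond routine care, Protocol 8.6.2.2 lets a routine gas within a 2-hour window stand in, and an infant never dosed may have no pre-dose value. The protocol supplied is version 2.0, while the SAP refers to later versions, so later collection rules cannot be seen.
- **The SF model is a weak precedent.** SAP 17.4.4.2 adjusts SF for its own baseline. That shows the 0-hour value is expected to be available, not that the SAP accepts it as a predictor of ventilation time.
- **The t-test comes first.** If it is the primary analysis, a new covariate in the mixed model would leave the primary result unchanged.

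These points limit the size of the claim and require a more careful amendment. They do not remove the reason for it: the data are already planned, a link to the endpoint is plausible, and the cost is close to nil if that link is absent.

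**Conclusion.** The point holds as a missed efficiency opportunity. The adjusted model omits a severity index that is scheduled before the first dose and already derived. For a partial correlation of 0.2 to 0.5, the gain is about 1 to 6 points of power and an interval 2% to 13% narrower; at zero there is effectively no change. This rests on the plan's own log-normal inputs, 134 analysed per group, an assumed correlation, and no infant being lost for want of a baseline value.

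A reader might conclude that the trial is underpowered or its primary comparison biased. Neither follows: the 90% power reproduces without adjustment, and randomisation protects the comparison.

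**What to change.** Amend SAP 17.4.1.2 before randomisation codes are released to the statistical team (the point named in SAP section 15):

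1. **Name the mixed model as the primary analysis**, since it is the one that meets Protocol 11.5, and keep the t-test as supportive.
2. **Add natural-log baseline OSI as a fixed effect**, with one definition: the 0-hour value, meaning the last value before the first intervention and before tracheal toilet or BAL; if no dose was given, the value nearest randomisation.
3. **Set a rule for missing values.** Infants with no such value receive the overall mean of the covariate, calculated ignoring arm, so that no randomised infant is dropped. State this as an exception, for baseline covariates only, to the rule against imputation in SAP 17.1.
4. **Add baseline OSI to the table in SAP 17.2.**

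Entering prior MV hours as a continuous term beside the stratum is optional; no gain has been quantified for it.

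The cost is a short SAP amendment and a small change to the analysis code, with no new data. Version 2.0 of the SAP already added a subgroup analysis without knowledge of allocation, so a blinded amendment has a precedent. One small drawback remains: because Protocol 8.1 allows two hours from randomisation to the first intervention, the 0-hour value may be read up to about 2 hours after randomisation, though still before treatment.
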